#### Alternate Training Sites:

##### *Community Rowing Inc. as an additional training site*

After subjects have completed screening and initial leg muscle strengthening, and have advanced in their training to the point at which they demonstrate sufficient knowledge and skill level at performing the FES-RT or arms-only-RT they may begin training at our alternate training site, Community Rowing Inc (CRI). There will be a SRH staff member on-site at CRI to supervise all FES-row or arms-only row training sessions. Also, only subjects who have demonstrated the ability to transfer onto the rower safely with minimal assistance will be allowed to perform the FES-RT or arms-only-RT at CRI. (There is not a lift system available at CRI.) All Laboratory visits will continue to be performed at Spaulding Hospital Cambridge or Spaulding Charlestown.

##### *Home Rowing as an additional training site*

Subjects who own an adapted rowing machine may perform some or all of their row training at home. Home rowing will only be allowed after subjects have completed screening and have advanced in their FES-RT or arms-only-RT to the point atwhich they demonstrate sufficient knowledge and skill in the use of the FES-unit and /or the adapted rowing machine and fully understand their individualized exercise program. All subjects must also demonstrate transfer competency on and off the rower with use of any assistance that they will have available at home. All Laboratory visits will continue to be performed at Spaulding Hospital Cambridge or Spaulding Charlestown.

Notes: There is no limit or specific requirement for training sessions that must be attended to continue participating in this protocol. Subjects, in all training groups, will be encouraged by study staff to attend three training sessions per week. Un-reported missed training session will be followed up with a phone call to document why the training session was missed and to encourage prompt return to training sessions as soon as possible.

Subjects who enroll before 3-months from their date of SCI will be given the opportunity

# PARTNERS HUMAN RESEARCH COMMITTEE

## DETAILED PROTOCOL

to participate in the FES-strength training during the period before study assessments begin after they reach 3-months post SCI. This will lessen leg muscle atrophy and allow faster progress in FES-row training when they enter that phase of the study.

### **Study Assessments**

Most Assessments will be performed at baseline and after 3 and 6 months for each study group. The DXA measurements and the AO-VO2max test (for the FES-RT group only) will only be performed at baseline and after 6 months. The Arms-only-RT and Wait-list groups will immediately enter baseline FES-RT protocol after completing all study procedures required in their initial group. Their six month lab visit and DXA scan data will also be used as their baseline FES-RT measures. Subjects may be asked to repeat any of the study assessments if there is difficulty obtaining results that meet our quality standards or there are equipment issues that arise.

Subjects that take longer than eight weeks to progress to performing their baseline FES-VO2max test will perform an extra assessment around the time of their baseline FES-VO2max test to account for changes that may occur over that time period. This extra study session will consist of: height, weight and circumference measures, blood samples, health questionnaires, pulmonary function tests, resting cardiovascular hemodynamics and neck suction-baroreflex testing. This extra testing session will take about 2-hours and can be done on a normal training day.

### Study Procedure Time Line:

	Baseline	3-Month	6-Month	Baseline-RT	3-Month-RT	6- Month-RT
FES-RT Acute and Chronic	FES-VO2max AO-VO2max Lab Visit DXA Scan	FES- VO2max Lab Visit	FES-VO2max AO-VO2max Lab Visit DXA Scan	N/A	N/A	N/A
AO-RT Acute	AO-VO2max Lab Visit DXA Scan	AO-VO2max Lab Visit	AO-VO2max Lab Visit DXA Scan	FES-VO2max	FES- VO2max Lab Visit	FES-VO2max Lab Visit DXA Scan
Wait list Acute	AO-Vo2max Lab Visit DXA Scan	AO-VO2max Lab Visit	AO-VO2max Lab Visit DXA Scan	FES-VO2max	FES- VO2max Lab Visit	FES-VO2max Lab Visit DXA Scan

### **Measurements and Testing Protocols:**

#### **VO2max Testing**

For subjects in the arms-only-RT and FES-RT groups VO2max testing will be

## PARTNERS HUMAN RESEARCH COMMITTEE

### DETAILED PROTOCOL

performed on a day scheduled for regular training. On-line computer-assisted open circuit spirometry will be used to determine O2 consumption, CO2 production, and respiratory exchange ratio. Expired O2 and CO2 gas fractions will be measured with a paramagnetic O2 and infrared CO2 analyzers. Ventilation will be measured via a Hans Rudolph 3813 pneumotachograph. Subjects will perform FES-rowing or arms-only-rowing while increasing power output every 1 to 2 minutes until volitional exhaustion. Immediately after FES-rowing or arms-only-rowing has stopped at the end of the VO2max test, subjects will have a finger tip pricked with a safety lancet in order to get a drop of blood that will be used to measure peak lactate levels in whole blood. Peak lactate levels will be used to evaluate exercise intensity as well as to monitor training status. To ensure attainment of maximal exercise capacity, at least 3 of the following criteria will be met: 1) O2 consumption plateaus despite increasing workload, 2) respiratory exchange ratio equals or exceeds 1.10 at end exercise, 3) 85% age-predicted maximal heart rate is achieved, and 4) perceived exertion is rated at least 17 on the Borg scale of 6-20.

#### Lab Visit(s)

All lab studies will be performed in the morning. All subjects will be instructed to abstain from vigorous exercise for 2 days prior to each study to avoid autonomic and neuroendocrine effects of exercise. In addition, subjects will refrain from caffeine and alcohol for the previous 24 hrs, and be studied after a 12 hr fast.

#### Neck Suction- Baroreflex Testing:

We will rely on neck pressure and neck suction to evaluate carotid sinus baroreceptor function at rest and during a variety of conditions. This technique has been employed to safely study cardiovascular physiology in human since the 1950's. The subject's neck is sealed by a neck collar connected to a computer-controlled bellows (pressure/vacuum pump). The neck collar is cushioned with an airtight silicon rubber bladder that is independently sealed and positioned against the contour of the anterior lateral neck. The bellows is used to increase or decrease pressure inside the neck collar, effectively compressing or distending the carotid sinus in the neck and causing reflex changes in heart rate and muscle sympathetic activity. However, these responses are evanescent since aortic baroreceptors are not affected; therefore heart rate and sympathetic activity (and sometimes blood pressure) are changed for only a few beats with any level of stimulus. Carotid baroreceptor reflex responses will be elicited during held expiration by application of an external neck pressure and suction sequence. Subjects will hold a normal end-expiratory volume, which triggers an external neck pressure increase of +40 mmHg for 4 heart beats and subsequent, serial R-wave triggered reductions of 15 mmHg to a pressure of -65 mmHg. This sequence results in stepwise initial carotid sinus compression followed by distension, evoking stepwise reflex changes in heart rate and sympathetic

## PARTNERS HUMAN RESEARCH COMMITTEE

### DETAILED PROTOCOL

activity. For each baroreflex testing, this procedure is repeated seven times to provide an averaged reproducible carotid baroreceptor reflex response relation.

Echocardiography. We will use a portable, commercially available system (Vivid-I, GE Healthcare, Milwaukee, Wis.), for cardiac characterization. Images will be obtained after 20 minutes of rest. Conventional 2-dimensional, Doppler, and color tissue-Doppler imaging from standard parasternal, apical, and subcostal positions will be performed. All data will be stored digitally for post-study off-line data analysis (EchoPac, Version 6.5, GE Healthcare). Left ventricular and atrial cardiac chamber volumes will be calculated using the modified Simpson=s technique. LV mass will be calculated using the area-length method. Relative wall thickness, an index of LV geometry, will be defined as: [interventricular septal thickness (mm) + posterior wall thickness (mm)] / LV internal end-diastolic diameter (mm). Myocardial tissue velocities (diastolic function) will be measured off-line from 2D color-coded tissue Doppler images and reported as the average of 3 consecutive cardiac cycles. Strain, strain rate, and LV rotational (systolic function) assessment will be performed by speckled tracking analysis. Peak global strain will be calculated as the average strain in the basal, mid, and apical LV as measured in the apical 4-chamber view. Atrial volumes will be calculated using the bi-plane area-length method. Right ventricular diastolic area, systolic area, fractional area change, tissue velocities will be measured. Measurements will be indexed for body surface area when appropriate.

Note: Subjects may also have their echocardiogram test performed at the Heart Center at Massachusetts General Hospital (MGH) if the cardiologist can be scheduled for a more convenient time for them at MGH than at Spaulding Cambridge. We will pay for parking if they choose to go to MGH for their echocardiogram.

Note: As of 1/1/19 we will no longer be able to measure any further echocardiogram tests in this protocol.

Resting Cardiovascular Hemodynamics: Heart rate and blood pressures will be measured after a 15-minute period of quiet supine rest. Heart rate will be measured by a standard 12-lead ECG and blood pressure by an automated sphygmomanometer. There will be a short period of time paced breathing in which subjects follow an audio cue to breath at a rate of 15 breaths per minute.

Pulmonary Function Tests: Spirometry will be used to measure lung function, specifically the measurement of the amount (volume) and/or speed (flow) of air that can be inhaled and exhaled. Specifically, Forced Volume Vital Capacity

## PARTNERS HUMAN RESEARCH COMMITTEE

### DETAILED PROTOCOL

(FVC) and Maximum Voluntary Ventilation (MVV) tests will be administered.

Height, Weight, and Circumferences: Weight will be measured on a scale. Height will be measured in the supine position with a tape measure. Circumferences of the waist, hip, abdomen, and thigh will be measured with a tape measure in the supine position.

Blood Samples: 70 ml of blood via venipuncture will be taken. Standard assays will include measures of insulin sensitivity and serum lipids. The homeostasis model assessment (HOMA) of insulin resistance, the quantitative insulin check index (QUICKI) and the serum insulin-like growth factor binding protein-1 (IGFBP-1) will be assessed. Plasma total cholesterol, low density cholesterol, high density APOa lipids, and triglycerides will also be measured. Other assays will include: total testosterone, calculated free testosterone, CBC, high sensitivity (hs) C-reactive protein, hemoglobin AIC, prealbumin and zinc. Blood work will be sent to Quest Diagnostics for analysis.

ASIA and Ashworth exams: Standard physical exams will be performed by a physician to categorize injury level and degree of spasticity.

Note: The ASIA and Ashworth exams will only be performed at Screening Visit 1 and 6-month and 12-month time points.

PROMIS 57 Questionnaire: The PROMIS 57 questionnaire will be used to assess changes in subject's views on their physical, psychological, and social well-being. The PROMIS 57 scales include eight items from seven primary PROMIS domains: depression, anxiety, physical function, pain interference (and one pain intensity item), fatigue, sleep disturbance and satisfaction with social roles.

PROMIS Cognition Short Form: a brief well validated self-report measure to assess perceived cognitive functioning.

The Patient Health Questionnaire (PHQ-9): a brief, well validated depression screening test that is widely used in medical research.

NIH Toolbox Meaning and Purpose Short Form: is a 7 item questionnaire that measures a person's sense of meaning and purpose in life over the past 7 days.

Craig Handicap Assessment and Reporting Technique Short Form (CHART-SF): is valid, reliable, and widely used in rehabilitation research to measure various community integration in people with various neurological conditions. We will be

## PARTNERS HUMAN RESEARCH COMMITTEE

### DETAILED PROTOCOL

collecting data on the Physical Independence, Mobility, Occupation, and Social Integration subscales.

SCI Exercise Self- Efficacy Scale (ESES): is a reliable and valid measurement of self-efficacy, or belief and confidence in one's skill and ability, to engage in physical activity.

#### DXA Scan(s)

A licensed radiology technician will perform all DXA scans. We will use a 5th generation GE Healthcare iDXA dual x-ray absorptiometry (DXA) scanner with enCore configuration version 12.3. For regional fat measurements, the DXA software can be used to define standard regions that will allow comparability of measurements throughout the study. DXA-derived visceral adipose tissue will be measured from a 5 cm slice placed across the entire abdomen above the iliac crest at the 4th lumbar vertebrae. Although DXA measures both visceral and subcutaneous fat, on each side of the abdominal cavity DXA can directly measure subcutaneous fat. The location of the abdominal cavity is detected by the gray scale change as the tissue contains lesser fat due to abdominal wall muscles. Subcutaneous fat over the visceral cavity is estimated from the DXA measurement of subcutaneous fat on each side of the abdominal cavity. The total estimated subcutaneous fat is subtracted from the total abdominal fat for DXA-derived visceral adipose tissue. This approach has been shown to performed as well as a clinical read from a CT scan. The precision of regional fat measures is  $\pm 1\%$ .

Note: If a DXA scan has recently been performed at Spaulding Rehabilitation Hospital and the results can be obtained, those medical records may be used and the baseline DXA scan will not be necessary.

## VI. BIOSTATISTICAL ANALYSIS

Power analysis: Based on longitudinal exercise capacity data from our lab, extensive sets of power analyses were performed. For the main analysis (acute subjects only), there will be 3 groups of subjects (FES-RT, wait-list and arms-only-RT) and measures at baseline, 3 months, 6 months, except for visceral adiposity (only at baseline and 6 months). The primary analysis (below) will include the three groups and will have as predictors two indicator (dummy) variables for two of the groups, and indicators for the 3 month and 6 month time points and interactions between the time points and the group indicator variables; this will be estimated as a linear mixed model. The only random effect will be for subject. In addition, for the fourth aim, the analysis will only include those entered into FES-RT at the outset, i.e., the FES-RT with acute SCI and all

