*Primary data analysis:* The primary analysis will test whether the FES-RT has 'better' values of the outcome variables at 6 months post-baseline. A general linear mixed model with a random effect for subjects will be used to conduct an intent-to-treat analysis. The main predictors will be indicator variables for group with the FES-RT group as the reference group and indicators for each of the other two groups, the time at which the outcomes were measured and treatment group by time interactions; menstrual status (with men coded the same as women who are not menstruating) will be included as a dummy variable; for the insulin resistance measure, body weight/fat changes will be included as a predictor. In a secondary analysis, we will include interactions terms between the group indicators and the 3 month indicator. In addition, similar models to the above will be estimated for secondary outcomes.

*Checking and Sensitivity Analyses:* It is important to ensure that data idiosyncrasies do not impact the results and that the results are generalizable. We will check for systematic differences between the model and the data using graphs, such as comparisons of predicted and observed values of the outcome variable, and other standard diagnostics. An extension of this idea is to simulate new sets of data based on our model and use the simulated data as a reference test group by comparing this to the observed data; we do this to look for situations in which the data appear different

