## PARTNERS HUMAN RESEARCH COMMITTEE

### DETAILED PROTOCOL

from what we would expect by using the model to predict the data. We will also check whether any important predictors have been left out of the model, for example, gender or severity of SCI or level of SCI. These will be tested by including them in revised versions of the model and testing whether the model is substantively improved. It is also important to explore the ‘missingness’ of data. The model we plan to use assumes that missing data are “missing at random.” This can be checked in several ways including comparing the characteristics of observations with and without missing values. More importantly, we can check whether our results would change if the data is “missing not at random” in several ways. For certain outcome variables, it may be the case that subjects who are either at the high end or the low end are more likely to be missing. For example, people at baseline who are very fat or very lean may be more likely to drop out. This can be checked by using constrained multiple imputation where we constrain our imputations to one end of the adiposity range. Comparing the results based on the constrained imputation to the unimputed results gives us a sensitivity analysis.

A second type of sensitivity analysis was originally suggested by Rubin and has been extended by Carpenter, Kenward and White who suggest weighting each imputed result (rather than Rubin’s standard “rules” of averaging the results), where the weight depends on the assumed departure from the MAR assumption. This technique relies on the imputations covering a fairly wide range of values (we would use 100 imputations) but this can be checked and additional data sets imputed if the range is too narrow. Carpenter, *et al.*, provide a graphic method of checking whether the range is wide enough. Finally, if dropouts are much more common than missing an occasion and then returning, we will estimate a pattern-mixture model. However, if there are many people who miss the 3 month measure, but not the 6 month measure, we will not pursue this strategy. A fourth issue deals with the variance structure of the model. Our prime model assumes that the variances are the same across groups. This will be tested by estimating a model with heterogeneous variance structures by group (this is available in some statistical packages, including Stata or SAS).

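### For outcomes measured at three visits, the primary model's subject-only random effect understates the 6-month change standard error if correlation decays with time; the plan names no alternative covariance

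*Combined protocol and SAP*

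**What the plan says.** The power paragraph of VI. Biostatistical Analysis describes a linear mixed model with group indicators, "indicators for the 3 month and 6 month time points and interactions between the time points and the group indicator variables", and adds: "The only random effect will be for subject". The primary data analysis paragraph repeats the structure: "A general linear mixed model with a random effect for subjects will be used to conduct an intent-to-treat analysis". Neither paragraph gives a residual covariance structure, a random slope, robust standard errors or a degrees-of-freedom method.

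On visits, Study Assessments states: "Most Assessments will be performed at baseline and after 3 and 6 months for each study group". The power paragraph makes one exception among the aim outcomes: "except for visceral adiposity (only at baseline and 6 months".

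On the test itself: "The primary analysis will test whether the FES-RT has 'better' values of the outcome variables at 6 months post-baseline". It is not said whether this means a difference in change from baseline or a difference in level at 6 months. The same paragraph then says: "In a secondary analysis, we will include interactions terms between the group indicators and the 3 month indicator". That can be read as leaving the 3-month interaction out of the primary model, although the power paragraph includes it.

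On the variance structure, the checking and sensitivity paragraphs say: "Our prime model assumes that the variances are the same across groups". The named check is a model with variances that differ by group. Graphs, standard diagnostics and comparison with data simulated from the fitted model are also planned, in general terms.

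**The concern.** A random intercept with independent residuals is a compound-symmetry model: the 0-3, 3-6 and 0-6 month correlations are equal and the variance is constant over time. The 6-month change contrast depends on the 0-6 pair alone, but the model estimates its variance by pooling all three pairs. In repeated physiological measurements, pairs 3 months apart are often more alike than pairs 6 months apart. When they are, the pooled value is too small for the 6-month change.

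The protocol gives some reason to expect this. Acute participants are assessed from 3 months after injury and enrolled up to 12 months after it. Aim 4 expects adaptation to depend on injury duration. Strengthening before rowing may take 2 to 12 weeks, and no minimum attendance is required. All of these suggest that participants will change at different rates, which makes the 6-month change more variable than the 3-month changes.

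At stake are the confidence intervals and error rates for FES-RT against wait-list and against arms-only-RT on the three-visit outcomes of Aims 1 to 3, and on secondary outcomes, for which similar models are planned.

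**Working it through.** **Inputs from the documents** (VI. Biostatistical Analysis): alpha 0.05, taken here as two-sided because the plan does not say; baseline-to-6-month correlation r06 of about 0.7, with 0.25 mentioned as a very different value; 50 acute participants split 20/15/15.

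**Inputs assumed**: the 0-3 and 3-6 correlations, taken as equal and called r_adj; equal visit variances (set to 1); complete data.

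**The plan's own figures.** 50/(1 − 0.15) = 58.8, so 59 against the 60 stated; 40%, 30% and 30% of 50 give 20, 15 and 15. Both agree with the plan. The statement that power is sufficient cannot be reproduced, because no effect size, standard deviation or power value is given.

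**Formulas.**
- True variance of a 0-6 change: V = 2(1 − r06) = 2(0.3) = 0.600.
- Random-intercept estimate: M = mean of the three pairwise change variances = [4(1 − r_adj) + 0.600]/3.
- Ratio of model to true standard error: q = √(M/V). The group-size factor 1/20 + 1/15 cancels.
- Two-sided type I error: 2[1 − Φ(1.96q)].

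**Results with r06 = 0.7.** The last column is the rejection rate of the random-intercept model in 40,000 simulated trials per scenario with 20/15/15.

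| r_adj (assumed) | M | q | Error, formula | Error, simulated |
|---|---|---|---|---|
| 0.60 | 0.733 | 1.11 | 3.0% | 3.0% |
| 0.70 (equal) | 0.600 | 1.00 | 5.0% | 5.1% |
| 0.75 | 0.533 | 0.94 | 6.5% | 6.4% |
| 0.80 | 0.467 | 0.88 | 8.4% | 8.3% |
| √0.7 = 0.837 (first-order decay) | 0.418 | 0.83 | 10.2% | 10.1% |

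With first-order decay and the plan's alternative r06 = 0.25 (r_adj = 0.50), the mean correlation is (0.50 + 0.50 + 0.25)/3 = 0.417, q = √(0.583/0.75) = 0.88 and the error is 8.4%.

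**Direct estimation.** A t-test on the 0-6 change with 47 degrees of freedom, which for this contrast stands in for an unstructured covariance when data are complete, rejected 4.9% to 5.1% of the time in every scenario.

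**Different rates of change.** Start from equal correlations of 0.7 and add a person-specific slope whose 6-month variance is s. Then V = 0.6 + s, and each 3-month change has variance 0.6 + s/4.
- s = 0.1: M = (2 × 0.625 + 0.700)/3 = 0.650, q = 0.96, error 5.9%.
- s = 0.3: M = (2 × 0.675 + 0.900)/3 = 0.750, q = 0.91, error 7.4%.

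Simulation gave 5.8% to 7.3%.

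**If the 3-month interaction is left out.** The contrast becomes 6 months against the mean of baseline and 3 months. Under first-order decay with r06 = 0.7:
- True variance: 1 + ¼(2 + 2 × 0.837) − (0.7 + 0.837) = 0.382.
- Model variance: 1.5(1 − 0.791) = 0.313, where 0.791 is the mean of the three correlations.
- q = √(0.313/0.382) = 0.91, error 7.6%.

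**Visceral adiposity.** Two visits have only one correlation, so a random intercept imposes no equal-correlation constraint. The simulated error was 4.9% to 5.1%.

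**The case against.** The strongest reply is that the harm is conditional. The documents give no correlation involving the 3-month visit, and the assumed range covers a conservative test (3%) as well as a liberal one (10%). The upper figure comes from pure first-order decay, which leaves no room for visit-level measurement noise, and noise pulls the structure towards equal correlations. If half of the 0.30 unshared variance were such noise (an assumption), the adjacent correlation would be about 0.77, the standard-error ratio about 0.92 and the error about 7.2%. This stands: a range should be reported, not the extreme.

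Three further points also stand.
- Naming one random effect does not exclude a structured residual. Independent residuals are the usual default, so part of the problem is that the plan does not specify the residual structure.
- If the test is a difference in level at 6 months, it is not affected in this way under equal visit variances and complete data. The group by 6-month interaction, which the power paragraph lists, is a change contrast, but the primary analysis paragraph does not say which it means.
- The planned diagnostics and simulated-data comparisons could reveal a poor fit over time. A reader might infer that the plan contains no safeguard at all; that goes too far. What is missing is a check aimed at correlation over time and a stated fallback.

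A reader might also infer that all primary outcomes are affected. They are not: visceral adiposity is exempt. Echocardiography ends from 1/1/19 under the protocol's own note, so the complete-data figures may not describe wall thickness and diastolic velocity.

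**Conclusion.** The point holds conditionally, for outcomes measured at three visits. If correlation decays with time and residuals are independent, the standard error of the group by 6-month change contrast is about 6% to 17% too small for adjacent correlations of 0.75 to 0.84, and a nominal 5% test rejects about 6.5% to 10% of the time. Under first-order decay without the 3-month interaction the figure is about 7.6%. These figures assume complete data and equal visit variances, with r06 = 0.7 from the plan and the adjacent correlations supplied by assumption.

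The tempting stronger reading is that the trial's false-positive rate does exceed 5%, or doubles. The documents do not support it, because the correlations that decide the matter are not given and the error could also fall below 5%. Under these assumptions the estimated differences themselves are not biased. This is a should-fix point: the size is uncertain, but the remedy costs little.

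**What to change.** In the power and primary data analysis paragraphs of VI. Biostatistical Analysis:

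1. For three-visit outcomes, replace the subject-only random effect with an unstructured within-subject covariance over baseline, 3 and 6 months (six parameters), fitted by REML with Kenward-Roger or Satterthwaite degrees of freedom. Keep the random-intercept model as a sensitivity analysis.
2. Name the primary contrast as the group difference in change from baseline to 6 months.
3. Reconcile the two paragraphs on whether the group by 3-month interaction is in the primary model.

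Visceral adiposity needs no change of covariance, only the small-sample degrees of freedom.

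The cost is wording only. If equal correlation is exactly true, complete-data error degrees of freedom fall from 94 (2 × 47) to about 47 (50 − 3). The critical t rises from 1.986 to 2.012, and 2.012/1.986 = 1.013, so intervals widen by about 1%.
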